1 PROTOCOL SUMMARY

1.1 SYNOPSIS

Title:	Deprescribing: a portrait and out-comes of the reduction of Polypharmacy in Portugal (DePil17-20)
Study Description:	This study protocol comprises three phases. The first two phases will be nationwide and aim to evaluate the prevalence and patterns of polypharmacy and assess the barriers and facilitators of deprescribing perceived by older adults, as well as their willingness to be deprescribed and to self-medicate. The third and last phase will be a non-pharmacological randomised clinical study to measure the impact of enablement of older adults in their willingness to be deprescribed and related quality of life.
Objectives:	Primary Objective: Willingness to be deprescribed after the intervention Secondary Objectives: Quality of life after the intervention
Study Population:	Older adults (≥ 65 years) in Portugal
Description of Study	In the intervention group the investigators will give enablement tools and talks with their General Practitioners about how to issue the problem of polypharmacy.
Intervention:	
Study Duration:	36 months.
Participant Duration:	6 month.

1.2 SCHEMA

2 INTRODUCTION

Polypharmacy is defined as the simultaneous taking of five or more drugs. It's present in 30-70% of older adults (1) and it's a significant predictor of the risk of falls (2) and other iatrogenic complications (3), inappropriate prescriptions (4), reduced patient's adherence (5), drug interactions (6), hospital admissions (7) and mortality (8). It is estimated that at least 75% of this adverse event is potentially preventable (9).

It is necessary to distinguish between appropriate and inappropriate medications (10), because as people get older the benefit/risk ratio of medications changes meaning that medications that were once appropriately prescribed may have become inappropriate (11). Potentially Inappropriate Medications (PIMs) are those for which the harms outweigh the benefits (12). Available data indicate that 20 to 65% of older adults are taking at least one PIM, leading to a high risk of adverse drug reactions, morbidity and mortality (13). There is a lot of information available to guide prescribers to start and maintain drug therapies that are safe and effective, but there is lack of knowledge concerning its reduction and/or withdrawal so maintaining safety and effectiveness (3, 8).

Deprescribing can be defined as the withdrawal of PIMs, under medical supervision, with the objective of managing the polypharmacy and improving health outcomes (14). However, it isn't risk's deprived, it can cause abstinence syndrome, rebound effects, pharmacokinetic/pharmacodynamic changes in the metabolism of not interrupted drugs and recurrence of symptoms that were in treatment by the withdrawn drug (1, 2).

So the decision to deprescribe results from a careful weighting between the therapeutic objectives and the risk/benefit ratio (15, 16).

Several deprescribing processes have been proposed in the literature (2, 17) and involve revision of all actual medications, identification of inappropriate medications (considering harms and benefits of medication use in the individual and in the setting of life expectancy and care goals), prioritisation of medications for withdrawal, withdrawal of medications (often with tapering) and close monitoring and support and also with documentation of the improvement in health and quality of life and the reduction of adverse effects (18).

There are several tools which have been developed in order to aid identifying PIMs in older adults. The most commonly employed explicit tools are the Beers criteria and the STOPP/START criteria (Screening Tool of Older Person's Prescriptions and Screening Tool to Alert Doctors to Right Treatment) that are lists of medications which are generally inappropriate in older adults (or in the presence of certain conditions) due to an increased risk and/or decreased need/benefit. The STOPP/START criteria also offer a list of medications that should be initiated in older adults with certain conditions. However, there are also implicit tools, which are questions to take in account during our clinical judgement, to assess the medication appropriateness, for example the Medication Appropriateness Index (19).

Several studies have established that the implementation of a deprescribing process is feasible in practice (20, 21) and may result in favourable patient health and quality of life outcomes (22) and a few strategies seem effective or promising (23). Most of these studies are limited by variable methodologies, single settings, short follow-up periods and/or lack of clinical outcome measurements (24).

But there is inconsistent reporting of the patient willingness to have a medication deprescribed (2, 18). The direct involvement of patients and their caregivers in the choice and administration of drugs has long been known to be very important, but it isn't usually applied, so many patients complain about lacking this opportunity in the decision-making process (25, 26). It is assumed that older people generally do not like to take multiple medications, but there is also evidence that they may be reluctant to accept their doctor's proposal to stop some of them (13, 16, 18). So it's important to understand this incongruity between not liking to take multiple medications and reluctance to accept the proposal to stop them.

3 OBJECTIVES AND ENDPOINTS

Primary objective is to assess the enablement of older adults while being Deprescribed in the rise of Willingness to be Deprescribed.

Secondary objective is to assess the enablement of older adults while being Deprescribed in the rise of their Quality of Life outcome.

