Perception of medication will be evaluated using Portuguese general BMQ, the willingness to be deprescribed will be assessed with two open-questions (one to assess the facilitators and the other to assess the barriers), and the actual self-medication will be evaluated with an analogic visual scale (0 to 10) about the need to self-medicate and its justification.

For those not knowing how to write or read, someone of their knowledge, will fill in the open questions, with their answers.

In case of less than 5% of answers of the open questions, two patient groups will be invited to make a focus group asserting reasons for accepting deprescribing.

Phase III: impact of enablement of older adults in their willingness to deprescribe and quality of life

Design

Non-pharmacological randomised clinical study, intended to last for six months.

Setting

Primary Care Centres in Portugal will be randomly selected from six Health Centres of Centre of Portugal (Aveiro, Castelo Branco, Coimbra, Guarda, Leiria and Viseu)

Sample size

Will be created two groups with a minimum of 190 patients each (one will be the intervention group and the other the control).

Study procedures

This phase of the study is expected to start in September 2019 and will last for 6 months.

Again, GPs sampling will be made according to existing files and those who accept to participate will recruit their own patients. Patients from previous phases can be enrolled in phase III. Assuming that a GP will be able to include at least 6 patients, a total of 64 GPs has to be enrolled in the study. Enrolled GPs will be instructed to invite all older adult (≥ 65 years) patients attending to the primary care consultation to participate in the study during until obtaining the sample size and being randomized according to the table for study entry. The geographical areas of work, the Districts, will be randomized for entry into exposed and unexposed groups. Those patients willing to participate in the study must give written informed consent and present willingness and ability to comply with the study requirements.

Exclusion criteria: Being acutely unwell in the last three weeks, and refuse to participate.

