8 STATISTICAL CONSIDERATIONS

8.1 STATISTICAL HYPOTHESES

The investigators' hypothesis is that the intervention will result in statistical higher willingness to be deprescribed and better quality of life.

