8.3 STATISTICAL ANALYSES

Descriptive statistics will be computed for all variables together with 95% CI whenever relevant and applicable. Associations between qualitative-independent variables will be tested using χ^2 test. Comparisons between two or more independent groups regarding a quantitative variable are to be conducted using analysis of variance (ANOVA) or Kruskal-Wallis non-parametric test, if normality assumption is not met. ANCOVA may also be used to adjust for potential confounding factors. Associations between quantitative independent variables will be analysed using Pearson's or Spearman's correlation coefficient depending on normality assumption. All tests will be two-sided, considering a significance level of 0.05.

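### The primary outcome is a post-intervention level in the synopsis and a change in section 3; the two between-group comparisons can disagree because baseline adjustment is only optional

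*Protocol*

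**What the plan says.** The synopsis (section 1.1) gives "Primary Objective: Willingness to be deprescribed after the intervention". Section 3 gives "Primary objective is to assess the enablement of older adults while being Deprescribed in the rise of Willingness to be Deprescribed". The hypothesis in section 8.1 is that "the intervention will result in statistical higher willingness to be deprescribed and better quality of life"; it does not say whether the level or the change is to be higher.

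The Phase III part of section 4 supplies the comparator: "Will be created two groups with a minimum of 190 patients each (one will be the intervention group and the other the control". It also sets the unit of allocation: "The geographical areas of work, the Districts, will be randomized for entry into exposed and unexposed groups". The six districts form two groups of three.

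Section 8.3 lists tests by type of variable. For a quantitative outcome it plans "Comparisons between two or more independent groups regarding a quantitative variable", by ANOVA or Kruskal-Wallis, and adds that "ANCOVA may also be used to adjust for potential confounding factors". Baseline willingness is not named as a covariate, and no paired or before-after test is listed. The section closes with "All tests will be two-sided, considering a significance level of 0.05".

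The Phase III data-collection paragraph has measurements at a beginning and an end, but attaches them to Phase II.

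**The concern.** A level after the intervention and a rise in willingness are different outcomes, and the protocol gives each as its primary objective. Once willingness is measured at two times in two groups, both of these can be computed:

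- **Level:** end value, intervention minus control.
- **Change:** end value minus beginning value, intervention minus control.

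If the groups start equal, both have the same expected value. If they start apart, they do not, and one can show a benefit where the other shows none. Allocating six districts makes a starting gap more likely than randomising 380 individuals would. With the contrast left open, the choice could be made after the data are seen, and the stated 0.05 would no longer describe the error rate.

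**Working it through.** **Inputs from the protocol:** at least 190 patients per group (380 in all), six districts with three per group, two-sided 0.05. The protocol gives no score, SD, willingness rate, within-person correlation or intracluster correlation (ICC), so those below are assumptions. It also gives no power or error figure for either contrast, so there is none to reproduce.

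**1. Is a baseline gap plausible?** Assume 50% willing at baseline and 380/6 = 63.3 patients per district. The design effect is DE = 1 + (63.3 − 1) × ICC. The 95% chance range for the baseline difference is ±1.96 × √(2 × 0.25/190 × DE).

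| Assumed ICC | DE | 95% range |
|---|---|---|
| 0 | 1.00 | ±10 points |
| 0.01 | 1.62 | ±13 points |
| 0.02 | 2.25 | ±15 points |
| 0.05 | 4.12 | ±20 points |

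A gap of 15 points lies at the edge of the range for ICC 0.02 and inside it for ICC 0.05.

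**2. What does such a gap do?** Willingness rates are assumed; 190 independent patients per group; within-person correlation 0.3 to 0.7. The level uses the pooled two-proportion z-test. The change uses the difference in changes divided by its standard error.

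| Baseline, I v C | End, I v C | Level | Change |
|---|---|---|---|
| 40% v 55% | 55% v 57% | −2 points, p = 0.69 | +13 points, p = 0.001 to 0.03 |
| 60% v 45% | 62% v 50% | +12 points, p = 0.02 | −3 points, p = 0.44 to 0.62 |

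In each row one contrast is significant, and the other is not and has the opposite sign. Neither row is significant in both directions. Allowing for clustering would make the p-values larger.

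**3. Error rate if both contrasts are tried.** Assume a numeric score with equal SDs at both times and correlation ρ between beginning and end. Write D for a difference between group means in SD units, so SE(D) = √(2/190) = 0.1026. Then:

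- z for level = D_end / 0.1026
- z for change = (D_end − D_beginning) / (0.1026 × √(2(1 − ρ)))
- correlation of the two z values = (1 − ρ)/√(2(1 − ρ)) = √((1 − ρ)/2)

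The effect giving 80% power for the level is (1.960 + 0.842) × 0.1026 = 0.287 SD. The bivariate normal distribution of the two z values gives:

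| ρ | Correlation of z values | P(at least one p < 0.05), no effect | P(disagree on significance), effect 0.287 SD |
|---|---|---|---|
| 0.3 | 0.59 | 0.088 | 0.267 |
| 0.5 | 0.50 | 0.091 | 0.226 |
| 0.7 | 0.39 | 0.094 | 0.202 |

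At ρ = 0.5 the either-test error is 0.091/0.05 = 1.8 times the stated level.

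**4. What baseline adjustment does.** The model for level is end = a + b × group + c × beginning. Subtracting the beginning value from both sides gives change = a + b × group + (c − 1) × beginning. The group coefficient b is the same, so once the beginning value is a covariate the choice between level and change no longer affects the estimated group effect.

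**The case against.** The strongest reply is that this is loose wording that the analysis would resolve. Step 4 bears that out in part: with baseline willingness as a covariate the two contrasts coincide, and covariate choices are commonly left to an analysis plan, which is not shown here. So the problem is not separate from baseline adjustment. What stands is that the protocol states its primary objective in two incompatible ways, which is more than missing detail, and that the one device that would reconcile them is only permitted, and only for unnamed confounders.

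The figures are also open to challenge. The two open questions have no score, so a numeric outcome is assumed. Steps 2 and 3 treat patients as independent although districts are allocated. The 0.09 applies only if both unadjusted tests are run and the better one is reported. All of this stands as a limit on the size of the problem.

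Two stronger readings should be set aside. A reader might infer from section 3 that a before-after rise within the intervention group could count as the primary result, since the objective sentences name no comparator. The rest of the protocol does not support this: section 4 sets up a control group, and section 8.3 compares independent groups and lists no paired test. A reader might also infer that the two contrasts could be significant in opposite directions. The worked cases show only a significant result beside a null one, and only because the groups start apart.

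**Conclusion.** The inconsistency is real and worth correcting. Two between-group contrasts fit the protocol's wording, and without baseline adjustment they can lead to different conclusions when the groups differ at baseline. Trying both raises the null error rate to about 0.09. At an effect that gives 80% power for the level, they disagree on significance in about 20% to 27% of trials. Both figures assume a numeric score, 190 independent patients per group and a correlation of 0.3 to 0.7, and both ignore clustering. The plausibility of a baseline gap rests on an assumed 50% willingness and ICCs of 0 to 0.05.

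**What to change.** Use one sentence for the primary comparison in the synopsis, section 3 and section 8.1, for example: *The primary comparison is the difference between the intervention and control groups in willingness to be deprescribed at the end-of-Phase-III assessment, adjusted for baseline willingness.* In section 8.3, make that adjustment the planned primary analysis in place of an option.

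Reconcile the Phase III data-collection paragraph in section 4, which places the beginning and end measurements in Phase II, so that the baseline and end values are those of the trial.

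The cost is rewording in those five places. No extra patients or assessments are needed, provided the beginning and end measurements are indeed those of Phase III. The change does not make the outcome computable: a score or responder definition for the two open questions is still missing, and that is a separate problem.

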4 STUDY DESIGN

This is a three-phase study:

1. Cross-sectional, analytical study of the prevalence and patterns of polypharmacy, namely sociodemographic and clinical profiles (age, genre, area of residence and years of study) and about medication (number of drugs and their active component), in older adults attending Primary Care in Portugal.
2. Cross-sectional, triangulation study of older adults' perception of Barriers to and Facilitators of Deprescribing, Willingness to be Deprescribed and Willingness to Self-medicate.
3. Non-pharmacological randomised clinical study of the impact of enablement of older adults in their willingness to be Deprescribed and related Quality of Life.

Phase I: prevalence of polypharmacy in older adults attending primary care in Portugal

Design

Cross-sectional, analytical study.

Setting

Primary Care Centres in Portugal will be randomly selected from the five main-land Portuguese Healthcare Administrative Regions and two Autonomous Regions (Madeira and Azores), in order to obtain a national geographical representative sample.

Sample size

Since the prevalence of polypharmacy in older adults is unknown, we used as base of population all older adults in Portugal. For the study, we used a 95% confidence interval (CI) and a maximum precision error of 5%, so a minimum of 385 patients should be recruited.

Study procedures

This phase of the study starts in November 2017.

General Practitioners (GPs) sampling is made according to existing files of previous projects adherent GPs, in other epidemiological studies. After the selection of GPs, those who accept to participate will recruit their own patients. Assuming that a GP will be able to include at least 6 patients in a 3-week period, a total of 65 GPs will be enrolled in the study: 21 in North of Portugal (31.7%), 16 in Centre of Portugal (24.7%), 18 in Lisbon-Tejo Valley (27.4%), 5 in Alentejo (8.4%), 3 in Algarve (4.3%), 1 in Azores (1.6%) and 1 in Madeira (1.9%) in accordance with the distribution of Portuguese old adult population (≥ 65 years) in Portugal according with Pordata (www.pordata.pt).

Enrolled GPs will be instructed to collect all necessary data about all older adults (≥ 65 years) patients attending a primary care consultation during the period of study: 5 days on 3 consecutive weeks (Monday and Tuesday on week 1; Wednesday and Thursday on week 2; and Friday on week 3).

Data collection

The collection of the data will occur in November 2017.

GPs will be responsible for collecting all data about patients' sociodemographic characteristics, as well as morbidity and medication, during their consultations.

Data will be electronically stored in a database specifically designed for this study using MS Access 2010. Data will be encrypted and password protected. Information will be treated in strict confidentiality to protect the privacy of patients. The investigators will have no access to the data of the patient, except the one provided by the GP meaning that the only person to know who is being studied is the GP.

Before the collection of data, there will be online reunions with the GPs participating in the study.

Phase II: patients' perception of barriers to and facilitators of deprescribing, willingness to be deprescribed and actual self-medication in adult patients with polypharmacy attending primary care in Portugal

Objectives

To assert reasons and facilitators, willingness to be deprescribed and actual self-medication

Design

Cross-sectional, analytical study.

Setting

It will be the same of the phase I.

Sample size

A minimum of 385 patients will be included in phase II in order to obtain a sample with a 95% CI and a maximum precision error of 5%.

Study procedures

This phase of the study is expected to start in June 2018.

Again, GPs sampling will be made according to existing files and those who accept to participate will recruit their own patients. Patients from phase I can be enrolled in phase II. Assuming that a GP will be able to include at least 6 patients in a 3-week period, a total of 65 GPs has to be enrolled in the study, with the same distribution of the phase I. Enrolled GPs will be instructed to invite all older adult (≥ 65 years) patients attending the primary care consultation to participate in the study during 5 days on 3 consecutive weeks (Monday and Tuesday on week 1; Wednesday and Thursday on week 2; and Friday on week 3). Those willing to participate in the study must give written informed consent and present willingness and ability to comply with the study requirements.

Exclusion criteria will be: Being acutely unwell in the last three weeks, and refuse to participate.

Data collection

The collection of the data will occur in June 2018.

Patient's socio-demographic and clinical characteristics and medication will be registered using the same methodology as described in phase I.

Perception of medication will be evaluated using Portuguese general BMQ, the willingness to be deprescribed will be assessed with two open-questions (one to assess the facilitators and the other to assess the barriers), and the actual self-medication will be evaluated with an analogic visual scale (0 to 10) about the need to self-medicate and its justification.

For those not knowing how to write or read, someone of their knowledge, will fill in the open questions, with their answers.

In case of less than 5% of answers of the open questions, two patient groups will be invited to make a focus group asserting reasons for accepting deprescribing.

Phase III: impact of enablement of older adults in their willingness to deprescribe and quality of life

Design

Non-pharmacological randomised clinical study, intended to last for six months.

Setting

Primary Care Centres in Portugal will be randomly selected from six Health Centres of Centre of Portugal (Aveiro, Castelo Branco, Coimbra, Guarda, Leiria and Viseu)

Sample size

Will be created two groups with a minimum of 190 patients each (one will be the intervention group and the other the control).

Study procedures

This phase of the study is expected to start in September 2019 and will last for 6 months.

Again, GPs sampling will be made according to existing files and those who accept to participate will recruit their own patients. Patients from previous phases can be enrolled in phase III. Assuming that a GP will be able to include at least 6 patients, a total of 64 GPs has to be enrolled in the study. Enrolled GPs will be instructed to invite all older adult (≥ 65 years) patients attending to the primary care consultation to participate in the study during until obtaining the sample size and being randomized according to the table for study entry. The geographical areas of work, the Districts, will be randomized for entry into exposed and unexposed groups. Those patients willing to participate in the study must give written informed consent and present willingness and ability to comply with the study requirements.

Exclusion criteria: Being acutely unwell in the last three weeks, and refuse to participate.

Two groups will be created with a minimum of 190 patients each, one of which will be composed from patients from the region of Aveiro, Coimbra and Guarda and the other from patients from the region of Castelo Branco, Leiria and Viseu. In the intervention group we will give enablement tools and talks with their GPs about how to issue the problem of polypharmacy. The information given in this group will result from the knowledge obtained in phase II in the shape of small leaflets and other information materials to be made according to the best practice, to be given and remembered at scheduled times to the intervention group.

Data collection

The collection of the data will occur in the beginning and end of phase II.

Patient's socio-demographic and clinical characteristics and medication will be registered using the same methodology as described in phase I.

Perception of medication will be evaluated using Portuguese general BMQ, the willingness to be deprescribed will be assessed with two open-questions (the same as phase II), and the quality of life we will assessed with EQ-5D.

For those not knowing how to write, someone of their knowledge, will fill in the open questions.

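### The ±5-point precision stated for Phases I and II at 385 patients assumes a design effect of 1, although patients are recruited through 65 GPs at about six each

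*Protocol*

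**What the plan says.** Section 4, Phase I, gives the basis of the sample size as "Since the prevalence of polypharmacy in older adults is unknown, we used as base of population all older adults in Portugal". It then sets a 95% confidence level and "a maximum precision error of 5%, so a minimum of 385 patients should be recruited".

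Patients are not drawn individually. GPs who agree to take part recruit from their own patients, and the number of GPs follows from a workload assumption: "Assuming that a GP will be able to include at least 6 patients in a 3-week period", hence 65 GPs, allocated over seven regions (one each in Azores and Madeira). There is no upper limit per GP, since each is told to "collect all necessary data about all older adults (≥ 65 years) patients attending" on five set days.

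Phase II uses the same structure and size: "A minimum of 385 patients will be included in phase II in order to obtain a sample with a 95% CI", again with a 5% error and 65 GPs.

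Section 8.3 says "Descriptive statistics will be computed for all variables together with 95% CI whenever relevant and applicable". It lists the χ² test, ANOVA or Kruskal-Wallis, ANCOVA and correlation coefficients. It does not say how the intervals are computed. Neither section mentions a design effect, an ICC or the GP as a unit.

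**The concern.** The precision statement is worded as an upper bound on the error, but its number is valid only for independent patients. Patients of one GP share a prescriber, a practice and a locality, so for an outcome such as polypharmacy some positive correlation within GP is to be expected. Any such correlation widens the interval that a given number of patients can support.

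What is at stake is the stated accuracy of the Phase I national prevalence and of any Phase II proportion. Intervals computed as if patients were independent would also look more precise than they are.

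**Working it through.** **Inputs.** From section 4: 95% confidence (z = 1.96), error 0.05, n = 385, 65 GPs, at least six patients each. The proportion is not stated, but p = 0.5 is what yields 385. The ICC is not in the Protocol, so a range of 0.01 to 0.10 is assumed. Equal numbers per GP are assumed, and no gain is credited for the regional allocation.

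**Step 1: reproduce the plan's figure.** n = z² p(1−p)/d² = 1.96² × 0.25/0.05² = 384.15 (unrounded z), rounded up to 385. The match is exact, with no inflation for clustering. A finite-population correction does not change this: with an assumed population of 2,000,000 it gives 384.07, also 385.

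**Step 2: break-even ICC at the planned minimum.** 65 × 6 = 390, five above 385. With DE = 1 + (m−1) × ICC, the error stays within ±5 points only if 384.15 × DE ≤ 390. This gives ICC ≤ (390/384.15 − 1)/5 = 0.003.

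**Step 3: margin at 385 with six per GP.** Half-width = 1.96 × √(0.25 × DE/385).

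| Assumed ICC | DE | Half-width (points) | n that would restore ±5 |
|---|---|---|---|
| 0.01 | 1.05 | 5.12 | 404 |
| 0.02 | 1.10 | 5.24 | 423 |
| 0.05 | 1.25 | 5.58 | 481 |
| 0.10 | 1.50 | 6.12 | 577 |

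**Step 4: more patients from the same 65 GPs.** With n = 65m, the largest ICC that keeps ±5 is (65m/384.15 − 1)/(m − 1). The half-width that ignores the GP is 1.96 × √(0.25/n), and the true one is larger by √DE.

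| Per GP (m) | n | Largest ICC for ±5 | Half-width ignoring GP | Half-width, ICC 0.01 to 0.10 | √DE at ICC 0.05 |
|---|---|---|---|---|---|
| 6 | 390 | 0.003 | 4.96 | 5.08 to 6.08 | 1.12 |
| 8 | 520 | 0.05 | 4.30 | 4.45 to 5.60 | 1.16 |
| 10 | 650 | 0.077 | 3.84 | 4.01 to 5.30 | 1.20 |
| 20 | 1300 | 0.126 | 2.72 | 2.96 to 4.63 | 1.40 |
| 30 | 1950 | 0.141 | 2.22 | 2.52 to 4.38 | 1.57 |

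Two things happen as m grows. The true margin shrinks and can fall within ±5, while the gap between the true margin and one that ignores the GP widens.

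**Step 5: coverage, only if the GP is ignored.** 2Φ(1.96/√DE) − 1 gives about 94% to 89% at six per GP and about 92% to 68% at 30 per GP, for ICC 0.01 to 0.10.

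**Step 6: sensitivity to prevalence.** The Introduction says of polypharmacy "It's present in 30-70% of older adults". At 30% or 70%, p(1−p) = 0.21, so 385 patients hold ±5 up to DE = 0.25/0.21 = 1.19. At six per GP that is an ICC of 0.19/5 = 0.038.

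**Step 7: tests of association.** The inflation is roughly 1 + (m−1) × ICC of the factor × ICC of the outcome. For a factor that varies within GP, with assumed ICCs of 0.05 and 0.10 and m = 6, it is 1 + 5 × 0.05 × 0.10 = 1.025, which is negligible. It becomes material when the factor is common to a GP's patients, that is, when its ICC is near 1.

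**The case against.** The strongest reply is that 385 and six are both minima. GPs record every older attender on five days, so recruitment may well exceed the plan. With the number of GPs fixed, more patients per GP always narrows the true interval. A reader might infer from the missing design effect that the ±5 margin will not be delivered at all. The Protocol does not support that: at 30 patients per GP (an assumed figure) the margin is ±2.5 to ±4.4 points throughout the ICC range. The shortfall exists at or near the planned minimum only. This part of the reply stands.

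Other parts also stand:

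- The ICC is an assumption. At 0.01 to 0.02 and six per GP the excess is only 0.12 to 0.24 points.
- Phase II measures beliefs, open answers and a 0 to 10 scale. Correlation within GP may be smaller there than for prescribing, and nothing in the Protocol fixes it.
- A reader might infer that all the χ² tests would reject too often. Step 7 shows this applies mainly to factors shared within a GP, such as area of residence, and hardly to age, sex or years of study.
- A reader might infer that the reported intervals will have the reduced coverage of Step 5. Section 8.3 names no interval method, and an analysis plan not shown here could use cluster-robust ones.

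What does not stand is the view that the whole matter can be left to the analysis plan. A clustered analysis repairs coverage. At 385 patients and p = 0.5 it cannot bring the interval back to ±5 points for the assumed ICCs. The precision statement is in the Protocol itself.

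**Conclusion.** The point holds in a limited form. The 385-patient precision statement for Phases I and II takes patients as independent, while the plan recruits them through 65 GPs. At the planned minimum and p = 0.5, ±5 points requires an ICC of about 0.003 or less. For an assumed ICC of 0.01 to 0.10 the margin is about ±5.1 to ±6.1 points.

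That the figure has a design effect of 1 is certain, because it reproduces exactly. The size of the shortfall rests on the assumed ICC, on p = 0.5 and on about six patients per GP. It shrinks or disappears with more patients per GP, or with a prevalence well away from 50%. In larger clusters, the weight of the problem moves from the stated margin to any interval that ignores the GP.

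The matter concerns the descriptive precision of Phases I and II. It says nothing about the Phase III comparison, which carries both of the objectives in section 3. It should be corrected but does not undermine the study.

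**What to change.** In section 4, under Sample size for both phases, restate the margin with its design effect and the assumed ICC range. Possible wording: *385 patients in 65 GPs give about ±5.1 to ±6.1 percentage points for an ICC of 0.01 to 0.10, at a proportion of 50%.* For Phase II, note that the ICC of the belief outcomes may differ.

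In section 8.3, state that the Phase I and II 95% intervals, and tests of factors shared within a GP such as area of residence, take the GP as the cluster (survey or cluster-robust variance, or a mixed model). If region is used as a stratum, merge Azores and Madeira with another region, since one GP each gives no between-GP variance to estimate. If an analysis plan already specifies this, a cross-reference is enough.

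The cost is a slightly less favourable stated margin and somewhat wider intervals. No extra patients and no change in conduct are needed.
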